2.7.3 Impact assessment of potential unblinding

To assess impact of potential unblinding on evaluation of efficacy of ofatumumab on relapses, summary statistics of ARR (patient-based and time-based) will be displayed by subgroup defined by impact of potential unblinding and treatment group.

This analysis will be performed at Cut-off 1.

2.7.4 Handling of missing values/censoring/discontinuations

Missing data will not be imputed.

2.8 Safety analyses

Safety analyses during the study will be detailed below. All safety analyses will be based on the SAF for Cut-off 1 analysis and ESAF for Cut-off 2 and final analysis, unless explicitly stated otherwise.

Patients will be grouped by the actual treatment received. Safety data for the core part will be reported for the first time when the double-blind loading dose period has been completed by the last patient (Cut-off 1 analysis). Safety data for the extension part including Safety FU period

data will be reported for the first time when the last patient has finished 48 weeks of treatment (Cut-off 2 analysis). Safety data beyond the cut-off 2 will be reported separately.

Unless explicitly otherwise stated, for patients who entered Safety FU period, safety data will be reported up to and including the safety cut-off.

- For Cut-off 1 analysis, safety data reported up to safety cut-off, the latest visit date including Safety FU, or Week 24 visit date, whichever comes first.
- For Cut-off 2 and final analysis, safety data reported up to safety cut-off or the latest visit date including Safety FU, whichever comes first.

The assessment of safety will be primarily based on the frequency of adverse events (including death and non-fatal serious adverse events). Additional safety assessments include laboratory tests, physical examination (including examination of skin), vital sign measures, ECG evaluations and assessment of suicidality. Clinically significant findings in these additional safety assessments will be reported as adverse events and analyzed as such. In addition, all safety assessments will be summarized or listed as appropriate.

2.8.1 Adverse events (AEs)

Treatment emergent adverse events (TEAE) is defined as any adverse event which start on or after the day of the first dose of study drug.

TEAEs will be reported if their onset days are no greater than “time at risk for AE”. Similarly, serious TEAEs will be reported if their onset days are no greater than “time at risk for SAE”.

TEAE will be coded by primary system organ class and preferred term according to the Medical Dictionary for Regulatory Activities (MedDRA). The MedDRA version used for reporting the study will be described in a footnote.

Incidence of TEAEs will be summarized (number and percentage of patients reporting any TEAE by primary SOC, preferred term, and treatment group. Serious TEAEs, drug related TEAEs, TEAEs leading to premature discontinuation from study drug, TEAE leading to study drug interruption, and most common TEAEs ($\geq 5\%$ in any of the treatment groups) will be presented in a similar format as adverse events. In addition, incidence of TEAEs will be summarized by SOC, preferred term, and maximum CTCAE grade. Missing CTCAE grade will not be imputed. The CTCAE version 5.0 will be used.

For Cut-off 1 analysis, odds ratios (investigational drug vs. control) with 95% confidence intervals will be presented along with the summary of any TEAEs and the summary of serious TEAEs. Details in calculations of odds ratios and their 95% confidence intervals are provided in Section 5.7.1. Incidence of any TEAEs will be plotted by SOC, along with the odds ratio (and corresponding 95% confidence interval) for TEAEs in each SOC. Odds ratios provide appropriate inferences for events that are likely to occur at certain times (e.g., injection related reactions) while no constant risk over time is expected.

If a patient reports more than one adverse event within the same primary SOC, the patient will be counted only once with the maximum CTCAE grade at the SOC level, where applicable.

All AEs will be presented in listings.

The following summaries will be repeated for Cut-off 2 and final analysis:

- Overall TEAE
- TEAE by CTCAE grade
- Serious TEAE
- Drug-related TEAE
- TEAE causing study drug discontinuation
- TEAE leading to study drug interruption
- Serious TEAE causing study drug discontinuation
- Most common TEAE
- Infections and infestations TEAE

2.8.1.1 Adverse events of special interest / grouping of AEs

Incidence of adverse events of special interest as defined in the latest version of case retrieval sheet (eCRS) at the time of each cut-off will be summarized by risk name, level, and treatment group. For Cut-off 1 analysis, odds ratios and 95% confidence intervals presented. The exposure-adjusted incidence rate of TEAEs that fulfill the risk search terms as defined in eCRS will also be summarized by risk name, preferred term and treatment group. For Cut-off 1 analysis, incidence rate ratios and 95% confidence intervals presented. Similarly, separate summaries will be provided for serious TEAEs that fulfill the risk search terms as defined in eCRS. Additionally, incidence or any TEAEs that fulfill the search terms as defined in eCRS will also be summarized by risk name, level, and maximum CTCAE grade.

2.8.1.1.1 Injection reaction related AEs

Incidence of injection site reaction AEs and injection systemic AEs as collected in the relevant CRF pages will be reported as part of the AE summary tables as two preferred terms respectively.

Additionally, incidence of injection site reaction AEs and injection systemic reaction AEs will be reported separately for each injection and cumulatively for all injections at each cutoff.

Symptoms listed in the injection site reaction or injection systemic reaction CRF pages will be summarized by providing the number and percentage of patients with each of the symptoms and pre-specified grouping of symptoms as well as overall. These summaries will be provided on each injection and cumulatively for all injections.

For the injection site reaction, no grouping of symptoms will be specified. For the injection systemic reaction, symptoms will be grouped under 6 categories as defined below and the number and percentage of patients with at least one symptom reported under the category will be provided for each category as available.

- Skin/mucosal tissue symptoms: Rash, Urticaria, Pruritus general, Flushing
- Respiratory compromise: Dyspnea, Bronchospasm, Chest discomfort, Cough
- Related to change in vital signs: Hypotension, Hypertension, Dizziness, Tachycardia
- Gastrointestinal symptoms: Nausea, Vomiting, Abdominal pain, Diarrhea

- Musculoskeletal/connective tissue symptoms: Arthralgia, Myalgia, Back pain
- Other manifestations: Fever, Headache, Chills, Asthenia, Fatigue, and other

For above summaries, reaction/symptom start date and time will be compared with the injection date and time. Only reactions/symptoms within 24 hours after injections will be included (i.e., time to onset of reaction \leq 24 hours). The time to onset of reaction will be derived as (reaction start date/time – injection date/time).

For the injection systemic reaction, time to onset of the first symptoms after each injection will be summarized by cumulative hour intervals (i.e., 0 to 1, 0 to 2, 0 to 3, etc. until 0 to 24 hours). These summaries will be provided for each injection and cumulatively for all injections.

The proportion of patients with injection site reactions and the proportion of patients with injection systemic reactions will be plotted by treatment group against the injection sequence labeled by the visit weeks of the corresponding injection.

Patients with injection site reactions and the corresponding category of the combination of the 3 types (type 1: steroid, type 2: antihistamine, type 3: antipyretics/analgesics) will be listed by treatment. Specifically, 9 categories are defined as 1) no injection related premedication, 2) type 1, 3) type 2, 4) type 3, 5) type 1+ type 2, 6) type 1+ type 3, 7) type 2+ type 3, 8) type 1+ type 2+ type 3, 9) Any injection related premedication. The types 1 to 3 refer to protocol specified three types of injection related premedication as stated in Section 2.4.2.3.

A separate listing for injection site reaction AEs and injection systemic reaction AEs will be provided where all reported injection related reactions (IRR) (regardless of timing) will be listed along with the corresponding visit with injection and time to onset from the most recent injection as well as from Day 1. The listing will be sorted by injection of first occurrence of symptoms. Specifically, under the first injection, patients whose first IRR was associated with the first injection will be listed; within a patient all IRRs to all injections will be listed chronologically. Under the second injection, patients whose first IRR was associated with the second injection will be listed; similarly, within a patient all IRRs to all injections will be listed chronologically. The listing will continue with subsequent injections until all patients with IRRs are included in the listing.

The following analyses will be repeated for Cut-off 2 analysis:

- Line plots for proportions of injection-related symptoms
- Proportion of patients with injection systemic reactions
- Proportion of patients with injection site reactions

2.8.1.1.2 Liver safety related AEs

Standardized MedDRA Queries (SMQs) are groupings of terms from one or more MedDRA SOCs that relate to a defined medical condition or area of interest. They are intended to aid in case identification.

Standardised MedDRA Queries (SMQ) and preferred terms searches for drug-related hepatic disorders will be conducted. Results of these searches will be analyzed and presented in a similar format as other adverse events. In case of liver events, detailed listings will be provided.

SMQ Table: The number and percentage of patients experiencing adverse events categorized under the SMQ module drug-related hepatic disorders – comprehensive search (SMQ code 20000006, broad search) and its SMQ sub-modules will be reported.

SMQ-PT Table: The more detailed SMQ-PT table including the respective preferred term frequencies falling under the SMQ drug-related hepatic disorders – comprehensive search (SMQ code 20000006, broad search) and its SMQ sub-modules will be provided.

2.8.1.1.3 Drug-related adverse events for Japan package insert

For display in the Japan package insert, incidence rate of drug-related adverse events will be displayed.

2.8.1.2 Adverse events by onset period

Incidence of TEAE will be displayed by first onset period. The following periods will be displayed:

- Day 1 – Month 3 (Day 1 – Day 90)
- Month 3 – Month 6 (Day 91 – Day 180)
- Month 6 – Month 9 (Day 181 – Day 270)
- Month 9 – Month 12 (Day 271 – Day 360)
- Month 12 or later (Day 361 or later).

For each period, incidence of an AE will be the proportion of patients with the AE among patients “at risk”. As seen section 2.4.1, “time at risk” will be defined in two ways for overall AE and SAE. Then two types of summary will be provided:

- Incidence of overall AE by first onset period: This will be based on time at risk for AE. Then *no SAE will be counted if it is reported after safety cut-off* in this analysis.
- Incidence of SAE by first onset period: This will be based on time at risk for SAE.

This analysis will be performed only for Cut-off 2 analysis.

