2.1.1 General definitions

Study drug/treatment refers to the investigational drug Ofatumumab and placebo.

“Date of Cut-off 2” is expected as the date the last patient completes all assessments at Week 48 visit. If the last patient discontinues from the study prior to Week 48 visit, “date of Cut-off 2” is the last patient's last visit.

Date of first administration of study drug/treatment, or first date of study drug/treatment, is defined depending on the analysis purposes.

- For Cut-off 1 analysis and Cut-off 2 and final *efficacy* analysis, it refers to the date when the first dose of randomized treatment is administered.
- For Cut-off 2 and final *safety* analysis, it refers to the date when the first dose of ofatumumab is administered.

Date of last administration of study drug/treatment, or last date of study drug/treatment is defined by analysis time point.

- For Cut-off 1 analysis, it refers to the date when the last dose of randomized treatment is administered up to Week 24 visit.
- For Cut-off 2 analysis, it refers to the date when the last dose of treatment is administered up to the date of Cut-off 2.
- For final analysis, it refers to the date when the last dose of treatment is administered up to EOS visit.

Study day is defined as: if after first date of study drug, then (Study Day) = (Date) – (first date of study drug) +1; if before first date of study drug, then (Study Day) = (Date) – (first date of study drug); Study Day 1 is defined as the date of the first administration of study drug; there is no Study Day 0.

Duration of an event is calculated as (event end date) – (event start date) +1.

1 month is counted as 30 days unless otherwise specified.

Baseline is defined for each cut-off analysis.

- For Cut-off 1 analysis, and Cut-off 2 and final *efficacy* analysis, baseline is defined as the last non-missing result before or on the first date of study drug.
- For Cut-off 2 and final *safety* analysis, definition of baseline depends on each patient's treatment course in the study
 - For a patient continuously having ofatumumab across Core and Extension parts, baseline is defined as the last non-missing result before or on the first date of study drug.
 - For a patient switching the treatment from placebo to ofatumumab when entering the Extension part, baseline is defined as the dose date of ofatumumab at Week 24. *For analysis on vital signs*, the baseline is defined as *the pre-dose measurement* at Week 24.

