2.4 Treatments (study treatment, rescue medication, concomitant therapies, compliance)

2.4.1 Study treatment / compliance

Analyses detailed in this section will be performed for Cut-off 1 analysis, Cut-off 2 and final analysis.

For the core part and the extension part, duration of exposure to study drug is defined as (last dose date) – (first dose date) + 31 – sum[(j+1)-th injection date – j-th injection date - 31], where j and j+1 refer to consecutive injections with injection dates more than 31 days apart (as patients are scheduled to take the subcutaneous injections every 28+/- 3 days).

Duration of exposure to study drug of core part and extension part will be summarized by treatment with number and percentage of patients and by duration category (i.e., >= 1 week, >= 2 weeks, >= 3 weeks, >= 4 weeks, >= 8 weeks, >= 12 weeks, >= 24 weeks, >= 36 weeks, >= 48 weeks, >= 60 weeks, >= 72 weeks, until end of the study). The number of patient years of exposure is calculated as (the sum of the number of days of exposure for all

patients in the group)/365.25 and will be summarized for each treatment arm, and by stratification factor Japan vs non-Japan.

Time at risk is the censoring time used for estimating exposure adjusted incidence rate of SAEs or AEs in patients who did not experience the event of interest. For patients who have experienced the event of interest, the actual date of the SAE, or AE onset will be used. Time at risk corresponds to the time window used for adverse event reporting and can serve as a denominator to certain safety analyses (e.g. in exposure-adjusted incidence rates).

Table 2-10 includes definition of time at risk for AE and SAE for Cut-off 1 analysis. It will determine the “end date of the Core part” when all randomized patients completed their assessment during the Core part.

Table 2-10 Time at risk for AE and SAE: Cut-off 1 analysis

Category	For those who completed Week 24 visit	For those discontinued the study prior to Week 24 visit
Time at risk for AE	Number of days in the study from first date of study drug to Week 24 visit date	Number of days in the study from first date of study drug to the earlier date of the following: - Safety cut-off - “End date of the Core part”*
Time at risk for SAE		Number of days in the study from first date of study drug to “end date of the Core part”

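### The AE-by-onset-period table at Cut-off 2 ignores how much of each period was observed, so the switchers' later periods can show a fall that is not real

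*SAP*

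**What the plan says.** SAP 2.8.1.2 sets out the table: "Incidence of TEAE will be displayed by first onset period". There are four 90-day periods, the fourth being "Month 9 – Month 12 (Day 271 – Day 360"), and then "Month 12 or later (Day 361 or later"), which has no upper bound. The measure is: "For each period, incidence of an AE will be the proportion of patients with the AE among patients" at risk. Two versions are planned. For all AEs: "Incidence of overall AE by first onset period: This will be based on time at risk for AE". The SAE version uses time at risk for SAE. On timing: "This analysis will be performed only for Cut-off 2 analysis".

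The clock and its end are defined elsewhere. On the first date of study drug, SAP 2.1.1 says: "For Cut-off 2 and final *safety* analysis, it refers to the date when the first dose of ofatumumab is administered". A placebo patient's Day 1 in this table is therefore the Week 24 injection. SAP Table 2-11 ends time at risk for AEs at the earlier of the safety cut-off (100 days after the last dose) and the date of Cut-off 2, and time at risk for SAEs at the date of Cut-off 2. That is one calendar date, expected to be the last patient's Week 48 visit.

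SAP 2.4.1 introduces the quantity for another use: "Time at risk is the censoring time used for estimating exposure adjusted incidence rate of SAEs or AEs". SAP 2.8.1.1 plans such rates for events of special interest, but not by onset period. SAP 2.8.1.2 does not say how a patient who covers only part of a period is counted, or whether a patient with an earlier event remains at risk.

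**The concern.** A table by onset period is read across its columns to see whether AEs become more or less frequent with time on drug. That reading needs the columns to represent comparable observation. A proportion of patients does so only if those counted in each column were watched for about the same time. At Cut-off 2 they are not: a single calendar date cuts off later periods at different points for different patients, and the last period has no fixed length.

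Extended safety is an objective of the Extension part, and the Cut-off 2 analysis supports registration in Japan. This is the only planned summary of overall TEAE and SAE incidence by time on ofatumumab, and the final analysis does not repeat it with longer follow-up. A column that is low because few days were observed could be read as declining risk, and a real late increase could be masked.

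**Working it through.** The documents give no figure for this table, so there is none to reproduce. The check asks what it would show if the true risk never changed.

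**Inputs from the documents.** 90-day periods (SAP 2.8.1.2). Clock from first ofatumumab dose (SAP 2.1.1). End of time at risk (SAP Table 2-11). Extension treatment of 24 to 48 weeks (SAP 1.1), which implies an entry spread of at most about 24 weeks, or 168 days. Sixty patients randomized 2:1, so 40 continuous patients and 20 switchers.

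**Assumptions not in the documents.** Constant hazard of 0.5 per year, no dropout, visits on schedule, entry uniform over 168 days. At risk is read as event-free patients whose time at risk reaches the period.

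**Time at risk at Cut-off 2.** The last patient's Week 48 visit is 48 × 7 = 336 days after first dose, or study day 337. The first patient enrolled has 337 + 168 = 505 days. Switchers start 168 days later, so they have 169 to 337 days.

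**Formulas.** With d days covered, risk = 1 − exp(−0.5d/365.25). A full period gives 1 − exp(−0.1232) = 11.6%. If days covered are uniform on 0 to D, mean risk = 1 − (1 − exp(−a))/a, with a = 0.5D/365.25.

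**Switchers.**
- Month 3-6: 157/168 are fully covered. The other 11/168 average 84.5 days (10.9%). Weighted: 11.5%.
- Month 6-9: 157/168 = 93% reach it. Of these, 67/157 are fully covered (11.6%) and 90/157 are uniform on 0 to 90 days (5.9%). Incidence = (67 × 11.6 + 90 × 5.9)/157 = 8.3%. Mean coverage = (67 × 90 + 90 × 45)/157 = 64 days.
- Month 9-12: 67/168 = 40% reach it, uniform on 0 to 67 days, mean 33.5. a = 0.0917, giving 4.4%. None is observed for the whole period.

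**Continuous ofatumumab.** Periods through Month 9 are complete. In Month 9-12, 145/168 are complete and 23/168 average 78.5 days (10.2%), giving 11.4%. In the open-ended period, those who reach it are uniform on 0 to 145 days: a = 0.1985, giving 9.3%.

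| Group | M0-3 | M3-6 | M6-9 | M9-12 | Day 361+ |
|---|---|---|---|---|---|
| Switchers | 11.6% | 11.5% | 8.3% | 4.4% | none |
| Continuous | 11.6% | 11.6% | 11.6% | 11.4% | 9.3% |

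**Other entry patterns.**
- All enter together: continuous Month 9-12 covers 337 − 270 = 67 of 90 days (8.8%), and switchers' Month 3-6 covers 169 − 90 = 79 of 90 days (10.3%).
- All but the last patient enter at the start of a 24-week spread: the continuous open-ended period covers 505 − 360 = 145 days, and incidence rises to 1 − exp(−0.1985) = 18.0%.

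**If patients with an earlier event stay in the denominator.** Even with full coverage, each 90-day period is multiplied by the share still event-free at its start (0.884 per earlier period): 11.6, 10.2, 9.1, 8.0%. This affects both groups and does not depend on the cut-off.

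**Masking.** If the switchers' hazard truly doubled to 1.0 per year after Day 180, Month 6-9 would show (67 × 21.8 + 90 × 11.4)/157 = 15.8%, but Month 9-12 (a = 0.1834) only 8.6%, below the 11.6% of the first period.

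**With person-time.** Under a constant hazard, expected first events equal hazard × expected event-free time. First events over patient-years within a period therefore give 0.5 per year in every column.

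**The case against.** The strongest reply is that the distortion is narrow. Forty of the 60 planned patients are in the continuous group, whose 90-day periods are complete through Month 9 if patients stay and nearly flat to Month 12 under staggered entry. The clear effect sits in two periods for about 20 patients. About 19 switchers would reach Day 181 and about 8 would reach Day 271, so each shortfall is roughly half a patient. All of this stands.

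The switchers are not hidden by pooling either: SAP 2.1.4 already displays the two ESAF groups separately, and SAP 2.4.1 summarizes exposure and time at risk at Cut-off 2, though not per onset period.

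The partial-coverage bias also rests on a reading. Tying at risk to time at risk plausibly removes patients who never reach a period, and the SAP does not state that a patient seen for one day counts the same as one seen for 90. That is fair, but the alternative of counting only fully observed patients would leave no event-free switcher in Month 9-12. Some rule is needed.

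Finally, SAP 2.8.1 prefers odds ratios for events concentrated at certain times, whereas SAP 5.7.2 assumes constant intensity. Applying 5.7.2 within 90-day periods weakens that objection without removing it.

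A reader might infer that incidence on ofatumumab must appear to fall in later periods generally. The documents do not support that: it fails for the continuous group's 90-day periods under staggered entry, and the open-ended period can rise. Nor is this the plan's only view of safety over time. Injection reactions are shown by injection (SAP 2.8.1.1.1), and laboratory values, B-cells and immunoglobulins by visit window (SAP 2.8.3 and 2.8.3.2).

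**Conclusion.** The point holds in limited form. The measure has no adjustment for partial observation, and at risk per period is not defined. For switchers this produces an artificial fall, to about 8.3% in Month 6-9 and 4.4% in Month 9-12 against a true 11.6% per full period. For the continuous group the 90-day periods are little affected unless patients enter close together, and the Day 361 or later column is not comparable with the others in either direction. Separately, keeping patients with earlier events in the denominator would create a decline in both groups.

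The sizes depend on the assumed hazard, entry pattern and absence of dropout. The direction for a partly observed 90-day period does not: on this reading of at risk it can only be understated. Entry spread much beyond 24 weeks would sit badly with the 48-week limit on the Extension, although the Protocol's Table 6-1 footnote allows for visits after Week 72, so no conclusion rests on it. The table is descriptive, with no test or decision rule attached, so this is a modest improvement and not a threat to the trial's conclusions.

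**What to change.** In SAP 2.8.1.2:

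- Define at risk for each period as event-free patients whose time at risk reaches the start of that period.
- Beside the crude percentage, show the number at risk, the patient-years within the period, and the exposure-adjusted first-event rate with the exact Poisson interval of SAP 5.7.2. Count time from the start of the period, and stop it at first onset, the end of the period, or the end of the applicable time at risk in Table 2-11, whichever comes first.
- Close the last period at a fixed day, or interpret it only through its rate.
- Present the two ESAF groups already specified in SAP 2.1.4.

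The cost is SAP wording and one reprogrammed table; all dates are already collected. The drawback is imprecision. The switchers' Month 9-12 period would hold at most about 8 × 33.5/365.25 = 0.73 patient-years. With no events, the exact upper limit is 3.69/0.73, about 5 per patient-year. The rate removes the artificial trend but will not detect a late increase there. Showing the patient-years makes that limit visible.
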